10. DATA ANALYSIS

10.1. Data Quality Assurance

The PI will be solely responsible for the accuracy of the data. Single data entry will be performed with plans to check 10% of primary variables as a quality control. Single data entry error rates are slightly higher than 0.5% when performed by trained staff and the minimally improved error rate through double data entry is outweighed by substantial cost savings for single data entry.²⁵ Data anomalies will be reviewed by the PI and clarification and/or correction will be performed. Incomplete entries will be reviewed and corrected if information is available.

10.2. Data Entry and Storage

Data will be entered on a spreadsheet file located on the TIRR Memorial Hermann password-protected desktop computer of the PI located in a locked office in TIRR Memorial Hermann. After data from reports generated from the UDS are entered into the spreadsheet, they will be filed in a study binder in a locked drawer in the office of the PI with HIPPA information removed.

5 years after manuscript publication, the paper reports will be placed into the shredder bins for destruction.

11. SAMPLE SIZE AND STATISTICAL METHODS

11.1. Determination of Sample Size

For SA 1, safety, feasibility, compliance, we use as a convenient sample size. The preliminary data with 12 subjects have shown high compliance, lack of adverse events, and feasibility. So we believe 14 is sufficient and we will enrol 20 patients to account for non-compliance in the outpatient setting. This study will help us to determine effect size for future studies.

11.2. Statistical and Analytical Plans

This pilot study will serve as an earlier-phase developmental function that will enhance the probability of success in a larger subsequent randomization intervention trial.

In Aim 1, for safety, we hypothesize that there will be no unusual adverse events. However, because UTI is directly related to the bladder, we will focus on the occurrence of UTI. Based on literature, the overall rate of UTI in SCI is about 2.5 episodes per patient per year.¹⁸ As a result, we expect to see .2 episodes per patient during the 4-week study period. Based on that, we construct the stopping rules to stop at 20% UTI rate using lower 90% exact Blyth-Still-Casella confidence bounds. If the number of patients with UTI exceed 3 in the first 5 patients, 4 in the first 10 patients, or 5 in the 14 patients, then patient accrual will be paused pending a review by a medical advisory board comprised of SCI experts.

For feasibility and compliance, we will calculate descriptive statistics to determine the dropout rate and percent of adherence to the prescribed regimen as well as program satisfaction. If the dropout rate is less than 25%, and if subjects complete greater than 70% of daily TTNS use in the 4-week period, we will consider the study has high feasibility/adherence. If more than 80% of subjects report that they were satisfied with the program, then we will consider the study has high satisfaction.

In Aim 2, descriptive statistics will be provided for incontinence episodes, catheterization frequency, volumes voided, and anticholinergic-related side effects after the TTNS. The results along the time will be compared to baseline by paired t test, signed t test, or repeated measure methods when appropriate. Since this is an exploratory study and the efficacy of TTNS in this study will be further studied in future larger studies, Bonferroni correction will not be necessary. TTNS satisfaction will be based on the scores of a TTNS survey and descriptive analysis will be provided as well. We will also check the association between these changes from baseline, as well as bladder medication associations.

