2.3. Secondary Objectives

Secondary Objective 1: I-QOL scores will improve and incontinence episodes will reduce after TTNS compared to baseline.

Secondary Objective 2: The frequency of catheterization and the volumes voided will improve with TTNS compared to baseline based on bladder diary.

Secondary Objective 3: Anticholinergic side effects will be reduced based on survey after TTNS protocol.

2.4. Potential Risks and Benefits:

a. End Points - Efficacy

Specific Aim 1: No efficacy requirement for the safety and feasibility studied in specific aim 1.

Specific Aim 2: We expect improved I-QOL scores compared to baseline. As a pilot trial, we have not powered the study for this measure. Results from this study will provide effect size to power a larger study.

b. End Points - Safety

Urinary Tract Infection (UTI) risk:

We expect the rates of morbidity to be the same between those who participate and those who do not. However, because UTI is directly related to the bladder, we will focus on the occurrence of UTI. Based on literature, the overall rate of UTI in SCI is about 2.5 episodes per patient per year. As a result, we expect to see 0.2 episodes per patient during the 4-week study period. Based on that, we construct the stopping rules to stop at 20% UTI rate using lower 90% exact Blyth-Still-Casella confidence bounds. If the number of patients with UTI exceed 3 in the first 5 patients, 4 in the first 10 patients, or 5 in the 14 patients, then patient accrual will be paused pending a review by a medical advisory board comprised of SCI experts.

Bladder medication discontinuation risk:

- Worsened incontinence

Electric Stimulation Risks:

Electric stimulation is commonly performed on the extremities of those with spinal cord injury at the study institution. There are few adverse reactions to electric stimulation. The common ones include:

- Pain with electric stimulation: in these cases, the intensity is reduced until it is comfortable.
- Skin irritation: it is common for redness to occur on the skin at the site of the surface electrode. This typically dissipates within an hour of removing the electrode. In some cases, the redness remains the next day. In these cases, they are likely sensitive to the adhesive used and a hypoallergenic skin electrode will be provided.

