9.3. Safety Monitoring Plan

The Data Safety Monitoring Plan (DSMP) for the research study includes periodic statistical analysis on rates of morbidity of study participants compared to controls by the PI and the

statistician. Because of the rolling recruitment in the proposed protocol, we anticipate the number of recruited individuals will be sufficient for morbidity review quarterly.

Specifically, we will focus on the occurrence of UTI. We hypothesize that the rate of UTIs in TTNS group will be similar to the SCI population. Based on literature, the overall rate of UTI in SCI is about 2.5 episodes per patient per year. As a result, we expect to see 0.2 episodes per patient during the 4-week study period. Based on that, we construct the stopping rules to stop at 20% UTI rate using lower 90% exact Blyth-Still-Casella confidence bounds. If the number of patients with UTI exceed 3 in the first 5 patients, 4 in the first 10 patients, or 5 in the 14 patients, then patient accrual will be paused pending a review by a medical advisory board comprised of SCI experts.

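### The UTI pause rule uses a mean of 0.2 episodes per patient as a 20% share of patients, which makes its reference modestly lenient; reference and count should be in one unit

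*Combined protocol and SAP*

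**What the plan says.** The same text stands in 2.4b (End Points - Safety), 9.3 (Safety Monitoring Plan) and 11.2 (Statistical and Analytical Plans).

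- The background figure is an episode rate: "the overall rate of UTI in SCI is about 2.5 episodes per patient per year".
- It is scaled to the study period, still in episodes: "As a result, we expect to see .2 episodes per patient during the 4-week study period" (11.2; the same in 2.4b and 9.3).
- On that basis the plan sets "stopping rules to stop at 20% UTI rate using lower 90% exact Blyth-Still-Casella confidence bounds".
- The limits count patients: "number of patients with UTI exceed 3 in the first 5 patients, 4 in the first 10 patients, or 5 in the 14 patients". A pause therefore needs at least 4 of 5, 5 of 10 or 6 of 14 patients.
- The consequence is "then patient accrual will be paused pending a review by a medical advisory board comprised of SCI experts".

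No section converts episodes to patients, makes an assumption about repeat UTIs, or gives the chance of a pause at any UTI rate.

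**The concern.** A mean number of episodes per patient and a proportion of patients with an episode are different quantities. A patient with two UTIs adds two to the first and one to the second. The mean is therefore at least as large as the proportion, and a limit on patients set against the mean is too forgiving.

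This is the trial's only numeric safety threshold, and safety is part of Primary Objective 1. The trial has no randomised comparator (the randomisation section is marked not applicable), so the literature rate is the working yardstick. If the yardstick is in the wrong unit and the rule's sensitivity is not stated, the team cannot tell how much reassurance an uncrossed limit gives.

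**Working it through.** **Inputs.** From 11.2: 2.5 episodes per patient-year, a 20% reference, a 90% lower bound, looks at 5, 10 and 14 patients. From section 5: 4 weeks per subject. The distribution of UTIs per patient is not in the documents, so a range of assumptions is used.

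**1. The plan's own figures.** 2.5 × 4/52 = 0.192, which rounds to the stated 0.2.

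The Clopper-Pearson lower limit of a two-sided 90% interval is the 5% quantile of Beta(x, n − x + 1). Against 20%:

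| Look | Highest count without a pause | Lowest count with a pause |
|---|---|---|
| 5 | 3/5: 0.189 | 4/5: 0.343 |
| 10 | 4/10: 0.150 | 5/10: 0.222 |
| 14 | 5/14: 0.153 | 6/14: 0.206 |

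All three printed limits reproduce this way. With the named Blyth-Still-Casella bound at 90%, the looks at 10 and 14 reproduce (4/10: 0.188; 5/10: 0.213 to 0.268; 5/14: 0.163 to 0.185; 6/14: 0.224 to 0.243; the ranges reflect the tie convention). The first look does not: 3/5 has a lower bound of 0.247, already above 20%.

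**2. From episodes to patients.** With m = 0.192:

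- Poisson: 1 − exp(−0.192) = 0.175 (0.181 with m rounded to 0.2).
- Gamma clustering with shape k: 1 − (1 + m/k)^(−k) = 0.150, 0.161 and 0.168 for k = 0.5, 1 and 2.
- No repeat UTIs: 0.192. This is the upper limit, since the share cannot exceed the mean.

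**3. Pause probability of the printed rule.** Take the binomial count after 5 patients and keep the part at 3 or fewer. Add 5 patients and keep 4 or fewer. Add 4 patients and keep 5 or fewer. One minus what remains is the chance of a pause. Doubling the episode rate gives m = 0.385.

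| Assumption | Share at background | Pause | Share at doubled rate | Pause |
|---|---|---|---|---|
| Poisson | 0.175 | 0.03 | 0.319 | 0.30 |
| Gamma, k = 2 | 0.168 | 0.03 | 0.297 | 0.24 |
| Gamma, k = 1 | 0.161 | 0.02 | 0.278 | 0.19 |
| Gamma, k = 0.5 | 0.150 | 0.02 | 0.248 | 0.13 |
| No repeat UTIs | 0.192 | 0.05 | 0.385 | 0.50 |

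Under Poisson, a 50% chance of a pause needs about 2.5 times the background rate, and 80% about 3.6 times.

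**4. How much of this is the unit?** Change only the reference, from 20% to 17.5%:

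- Two-sided 90% Clopper-Pearson: 4/5, 5/10, 6/14 becomes 3/5, 5/10, 6/14. Only the first look moves (0.189 lies between 0.175 and 0.20).
- Blyth-Still-Casella 90%: 3/5, 5/10, 6/14 becomes 3/5, 4/10 and either 5/14 or 6/14, because the bound for 5/14 straddles 0.175.

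| Pause at | Background (0.175) | Doubled rate (0.319) |
|---|---|---|
| 4/5, 5/10, 6/14 (printed) | 0.03 | 0.30 |
| 3/5, 5/10, 6/14 | 0.06 | 0.35 |
| 3/5, 4/10, 6/14 | 0.10 | 0.45 |
| 3/5, 4/10, 5/14 | 0.12 | 0.54 |

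Correcting the reference lifts detection from 0.30 to 0.35 with the interval that reproduces the printed limits, and from 0.35 to between 0.45 and 0.54 with the named one.

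**5. Counting episodes.** Expected episodes at the looks are 5 × 0.192 = 0.96, 10 × 0.192 = 1.92 and 14 × 0.192 = 2.69. The exact Poisson lower limit of a two-sided 90% interval for c episodes is half the 5% quantile of chi-square with 2c degrees of freedom: 0.82, 1.37, 1.97, 2.61 and 3.29 for c = 3 to 7. The smallest counts that exceed expectation are 4, 5 and 7, which differ from the patient limits at the last look. Applying step 3 to Poisson counts, 4, 5 and 7 give a pause probability of 0.06 at background and 0.41 at the doubled rate. The printed 4, 5 and 6 applied to episodes would give 0.075 and 0.49, with 0.09 to 0.12 at background under clustering (k = 2 to 0.5).

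**The case against.** The strongest reply is that the slip is small. The gap is 2.5 percentage points under Poisson, of which about 0.6 comes from rounding 0.192 to 0.2, and the Poisson model is not in the documents. If nobody has a second UTI in four weeks, the share is 19.2% and the printed rule detects a doubled rate about half the time. If the share of patients itself doubles to 40%, it pauses in 54% of trials. Crossing a limit only pauses accrual for review, in a convenience-sample pilot that also has weekly calls (6.4), adverse event collection (9.2) and quarterly morbidity review (9.3).

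Most of this stands, and it rules out several stronger readings that a reader might infer:

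- *The unit slip is why a doubled rate would usually be missed.* Step 4 does not support this. With the interval that reproduces the limits, the correction adds only 5 points of detection.
- *The limits at 10 and 14 patients are each one too high.* This depends on the interval. Under two-sided 90% Clopper-Pearson neither moves; under Blyth-Still-Casella 4/10 would trigger and 5/14 is undecided.
- *Keeping the printed counts and counting episodes would suffice.* Those limits come from a bound on patients, so reusing them is a new mismatch. One patient with recurrent UTIs could then drive a pause.
- *The plan treats an uncrossed limit as proof of a normal UTI rate.* It does not say so. Section 9.3 states similarity to the SCI population as a hypothesis, apart from the rule.

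The reply does not remove the unit error itself, which is in three sections and errs lenient whenever repeat UTIs occur.

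**Conclusion.** The concern holds in a limited form. The reference is a mean of episodes used as a share of patients. The matching share is about 17.5% under Poisson, 15.0 to 16.8% with gamma clustering (k = 0.5 to 2), and at most 19.2%. The 20% figure is therefore modestly lenient.

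This contributes to a low chance of detecting a doubled episode rate, but the main causes are the 14 patients and the confidence level. All pause probabilities here assume independent patients, each followed for the full four weeks. That a doubled rate would more often be missed than caught is clear under Poisson or clustering, and close to even if there are no repeat UTIs.

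**What to change.** In 2.4b, 9.3 and 11.2, put the reference and the count in one unit, by one of two routes:

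- **(a) Count patients.** Set the reference to the expected share with at least one UTI (about 17.5%), state the distributional assumption, and recompute the limits with the interval actually used, named correctly. Under both two-sided 90% Clopper-Pearson and Blyth-Still-Casella, 3 of 5 would then trigger, against the printed 4 of 5 (under Blyth-Still-Casella this is so even at 20%). The later looks depend on the interval.
- **(b) Count episodes.** Derive the limits from an exact Poisson bound on 0.192 episodes per patient, as in step 5, and do not reuse the patient limits.

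With either route, state the pause probability at the background and doubled episode rates. At study end, report UTI episodes per patient-year with an exact Poisson 95% CI beside 2.5.

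The cost is a wording change in three sections and a short recalculation; no new data item is needed. Unnecessary accrual pauses would rise from about 3% to about 6 to 12%, depending on the route, the interval and the degree of clustering.

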3.6. Subject Replacement

Subjects who drop out will be replaced by recruitment from the SCI clinic and asking for informed consent from those who meet the I/E criteria.

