4. TRIAL SCHEDULE

Table 2. Timeline of protocol per subject

Weeks in Study Protocol

| Activities | 0 | W1 | W2 | W3 | W4 |
|--|---|---------|----|----|----|
| Clinic Enrolment: | | | | | |
| Eligibility screen | X | | | | |
| Informed Consent | X | | | | |
| Incontinence Questionnaire (I-QOL) | X | | | | |
| Side effect questionnaire | X | | | | |
| TTNS demonstration | X | | | | |
| Home | | | | | |
| Bladder diary | | □-----□ | | | |
| I-QOL | | | X | | X |
| TTNS | | □-----□ | | | |
| Discontinue bladder medication | | | X | | |
| Side effect questionnaire/ TTNS survey | | | | | X |

5. STUDY DESIGN (Table 2)

Anticipated number of patients to screen: 40

- Anticipated number of patient to enrol: 20
- Anticipated drop out or loss to follow-up: 4

Approximate time to complete study recruitment: 1 year

Expected duration of subject participation: 4 weeks

TTNS protocol: (please refer to protocol HSC-MS-15-0806) electrodes 2 inch by 2 inch will be placed according to anatomic landmarks, with the negative electrode behind the internal malleolus and the positive electrode 10cm superior to the negative electrode, verified with rhythmic flexion of the toes secondary to stimulation of the flexor digitorum and hallicus brevis. The intensity level will be set to the amperage immediately under the threshold for motor contraction. If there is not contraction seen, maximal tolerable intensity will be used. In addition, if the patient perceives pain, the intensity will be lowered until comfortable. Stimulation frequency of 10 Hz and pulse width of 200ms in continuous mode will be used.^{13, 14}

- Information gathered:
 - o Clinical demographics, morbidity, and Neurologic Exam findings from interview with subjects, exam, and EMR review.

- Bladder diary will include:
 - use of TTNS with amperage and presence of toe flexion, and pain score 0-10
 - log of catheterization, volumes
 - log of incontinence episodes
 - Description of other observed changes, including but not limited to: fatigue, vision changes, mental status, bowel program changes, and sexual function changes.
- Information will be tabulated on an Excel spreadsheet on my personal work desktop, password protected. Any paper data (bladder diary) will be de-identified and retained in a locked drawer in the locked office of the PI.

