6.4. Study Visits and Procedures

- *Screening Visits and Procedures*

Screening will be performed in the SCI clinic by the PI and co-I SCI attendings.

Those that meet the I/E criteria will be approached for the study by the PI and co-I attendings. They have until the study period is complete to decide whether they want to participate. However, they will have to return to clinic to have the TTNS trial performed and the directions for home use.

- *Study Visits and Procedures*

Subjects will have their first study visit after their normal clinic visit. Once consented, we will trial TTNS for a response of toe flexion. If they have a response, they will be included in the study. If no response or not tolerating electric stimulation, they will not be included in the study.

Participants will have direction in clinic on the use of the Stambil+, including written, oral, and smartphone images/video if they have access.

The electric stimulation protocol will use stimulation frequency of 10 Hz and pulse width of 200ms in continuous mode for 30 minutes daily, beginning as soon as possible. For sexually active women of child-bearing age, the home use will begin after the results of a pregnancy test are provided. The goal is daily use of TTNS for 4 weeks.

Subjects will be called weekly to capture the information from the bladder diary log and to monitor progress of protocol. They will also be reminded to change electrodes weekly.

- *Final Study Visit:*

Upon completion of the 4-week protocol, subjects will return with the stimulator and the bladder diary.

- *Post Study Follow up and Procedures*

The data will be statistically analysed in the post-study follow up. Subject participation is not required.

- *Discontinuation Visit and Procedures*

If withdrawal occurs, no evaluation will be required for the final study visit, regardless of the withdrawal reason. There are no safety risks in withdrawing from this study at any point.

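### The printed UTI pausing rule does not follow from the 90% Blyth-Still-Casella bound named as its source: the first count, the named method or level, or the word 'exceed' is wrong

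*Combined protocol and SAP*

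**What the plan says.** The rule appears with the same counts and the same derivation in sections 2.4b (End Points - Safety), 9.3 (Safety Monitoring Plan) and 11.2 (Statistical and Analytical Plans). On the derivation, section 11.2 states: "we construct the stopping rules to stop at 20% UTI rate using lower 90% exact Blyth-Still-Casella confidence bounds". On the trigger, it acts if patients with UTI "exceed 3 in the first 5 patients, 4 in the first 10 patients, or 5 in the 14 patients". On the consequence: "then patient accrual will be paused pending a review by a medical advisory board comprised of SCI experts".

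The 20% comes from a literature rate of 2.5 episodes per patient-year, taken as 0.2 episodes over four weeks. The documents print no bound values, do not say whether the 90% is one-sided or two-sided, and give no probability of triggering a pause.

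On who is counted, section 11.1 says "So we believe 14 is sufficient and we will enrol 20 patients to account for non-compliance in the outpatient setting". Section 5 gives "Anticipated number of patient to enrol: 20" and "Anticipated drop out or loss to follow-up: 4". Section 3.6 adds: "Subjects who drop out will be replaced by recruitment from the SCI clinic".

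**The concern.** Rate, level, method, sample sizes and counts are all printed, so the derivation can be checked from the documents alone, and it does not reproduce the rule. At 3/5 the 90% lower bound is already above 20%, yet the rule as worded does not pause at 3/5.

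This is the only numeric safety threshold in the plan. The IRB or the advisory board cannot tell which confidence level the rule carries, or whether the thresholds are those the authors meant. Depending on where the slip lies, the correction changes no threshold, the first one only, or all three.

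**Working it through.** **Inputs (sections 2.4b, 9.3, 11.2).** Reference rate p0 = 0.20; looks at n = 5, 10, 14; 'exceed' 3, 4, 5, so pause at X ≥ 4, 5, 6. The background figure reproduces: 2.5 × 4/52 = 0.192, rounded to 0.2.

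**Step 1. Exact upper tails at 20%**, P(X ≥ k | n, 0.20):
- n = 5: k = 3, 0.0579; k = 4, 0.0067
- n = 10: k = 4, 0.1209; k = 5, 0.0328
- n = 14: k = 5, 0.1298; k = 6, 0.0439

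**Step 2. Lower limit of a two-sided 90% Blyth-Still-Casella interval.** The method inverts the shortest sets of counts with binomial probability at least 0.90. At p = 0.20 the shortest set is unique at each look: {0–2} for n = 5 (0.942), {0–4} for n = 10 (0.967), {1–5} for n = 14 (0.912). The first high counts that exclude 20% are 3/5, 5/10 and 6/14. Lower bounds: 3/5, 0.247; 4/10, 0.188; 5/14, 0.163 to 0.185 by tie rule. A one-sided 90% Clopper-Pearson bound gives the same counts (3/5, 0.247; 5/10, 0.267; 6/14, 0.243). The printed first count is not reproduced; the other two are.

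**Step 3. Lower 90% read as 10% in the lower tail, from an 80% two-sided Blyth-Still-Casella interval.** Shortest 80% sets at p = 0.20: {0–2} for n = 5 (0.942); for n = 10 a tie between {0–3} (0.879) and {1–4} (0.860); {1–4} for n = 14 (0.826). First excluded counts: 3/5; 4/10 if the higher-coverage set is kept, otherwise 5/10; and 5/14. The 4/10 bound is 0.209 with the higher-coverage set and ranges from 0.158 to 0.240 by tie rule. The 5/14 bound is 0.216. With 4/10 these are the printed integers 3, 4, 5, but with 'at least' in place of 'exceed'.

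**Step 4. What does give ≥4/5, ≥5/10, ≥6/14?**
- One-sided 95% Clopper-Pearson (the lower limit of the equal-tailed 90% interval): 3/5, 0.189 and 4/5, 0.343; 4/10, 0.150 and 5/10, 0.222; 5/14, 0.153 and 6/14, 0.206. All three counts match.
- 95% Blyth-Still-Casella: shortest sets {0–3} (0.993), {0–4} (0.967), {0–5} (0.956). All three counts match.

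**Step 5. Chance of a pause.** First look, by hand:
- At 20%: P(X ≥ 4) = 5(0.2⁴)(0.8) + 0.2⁵ = 0.0067; P(X ≥ 3) = 10(0.2³)(0.8²) + 0.0067 = 0.0579.
- At 40%: P(X ≥ 4) = 5(0.4⁴)(0.6) + 0.4⁵ = 0.0870; P(X ≥ 3) = 10(0.4³)(0.6²) + 0.0870 = 0.3174.

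For later looks, carry forward the probability of each count below the boundary, add a Binomial(5, p) increment and then a Binomial(4, p) increment, and sum the mass at or above the boundary at each look. Cumulative chance of a pause after 5 / 10 / 14 patients:

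| Boundary | True 20% | True 30% | True 40% |
|---|---|---|---|
| 4/5, 5/10, 6/14 (as printed) | 0.7 / 3.5 / 5.6% | 3.1 / 15.5 / 24.7% | 8.7 / 37.3 / 54.3% |
| 3/5, 5/10, 6/14 (Step 2) | 5.8 / 7.3 / 9.0% | 16.3 / 22.5 / 29.9% | 31.7 / 45.0 / 58.6% |
| 3/5, 4/10, 5/14 (Step 3) | 5.8 / 13.8 / 18.0% | 16.3 / 37.3 / 47.8% | 31.7 / 63.6 / 76.2% |

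**The case against.** The best defence is that the rule works as printed. The integers agree in all three sections, they form a coherent set under another exact method or level, and crossing them only pauses accrual for expert review. If just the label is wrong, no pause probability changes. On the Step 2 reading two of the three looks already agree, and the whole-rule difference is 3.4 points at a true 20% rate (9.0 − 5.6) and 4.3 at 40% (58.6 − 54.3). All of that stands and limits the weight of the point. It does not repair the derivation, because 3/5 excludes 20% on both readings of sidedness.

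Three stronger readings are tempting, and the documents support none of them.
- A reader might infer that only the first count or the label can be wrong. That assumes the two-sided 90% reading. Sidedness is not stated, and Step 3 shows that 'exceed' may be the slip, in which case all three looks are affected.
- A reader might infer that the first look should pause at 3/5 and that the printed rule is too lax. Nothing in the documents shows which element was intended.
- A reader might infer that safety goes unmonitored after the fourteenth patient, since no count is printed beyond it. Section 6.4 keeps weekly contact ("Subjects will be called weekly to capture the information from the bladder diary log and to monitor progress of protocol"), section 9.3 plans quarterly morbidity review, and section 11.1 treats 14 as the sufficient number. A further look is a design preference.

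**Conclusion.** The point holds: the printed rule cannot be derived from the named method at 90% on either reading of sidedness. The first count, the method or level, or the word 'exceed' is wrong, and the documents do not settle which.

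The size depends on the answer. If the label is wrong, nothing changes in operation. If the first count is wrong, the first-look chance of a pause moves from 0.7% to 5.8% at a true 20% rate and from 8.7% to 31.7% at 40%, while the whole rule moves only to 9.0% and 58.6%. If the inequality is wrong, the whole rule moves to 18.0% and 76.2%. It should be fixed, but it does not prevent the trial from being run.

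The pause probabilities assume independent patients with a common UTI risk, each counted once, and looks at exactly 5, 10 and 14. The n = 10 count in Step 3 depends on the tie rule. The first-look mismatch depends on neither sidedness nor tie rule, and using the unrounded 0.192 does not remove it, since the 3/5 bound is 0.247.

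**What to change.** In sections 2.4b, 9.3 and 11.2, reconcile the counts, the inequality and the named method in one step. State the confidence level, the sidedness and, where it matters, the tie rule that reproduce all three counts, and give the resulting pause probabilities at a few true rates. Do not simply reword to 'at least k' first: until k is re-derived, an editor could equally write 3, 4, 5 or 4, 5, 6.

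As a minor addition, say whether the looks count enrolled or evaluable patients, given 14 judged sufficient, 20 enrolled, 4 expected losses and replacement of dropouts.

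The cost is wording in three places. If the label is corrected, the rule behaves exactly as now. If the counts or the inequality change, the chance of an accrual pause at a true 20% rate rises from 5.6% to between 9.0% and 18.0%.

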2.2. Primary Objectives

Primary Objective 1: Safety, feasibility, and compliance of TTNS at home.

Primary Objective 2: Overall satisfaction with TTNS based on survey.

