3.5. Withdrawal Criteria

Possible reasons for discontinuation of study intervention:

- Intolerable incontinence after discontinuation of bladder medications
- Intolerant to electric stimulation
- Non-compliance

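### Compliance is a primary outcome with no stated denominator, while non-compliers may be discontinued and replaced, so the >70% adherence bar may be met after poor adherers have left

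*Combined protocol and SAP*

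**What the plan says.** Section 2.2 puts compliance among the primary questions: "Primary Objective 1: Safety, feasibility, and compliance of TTNS at home". Hypothesis 1.1 (section 2.1) expects it to be high.

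Section 11.2 describes the analysis: "we will calculate descriptive statistics to determine the dropout rate and percent of adherence to the prescribed regimen". It then gives a joint pass mark: "If the dropout rate is less than 25%, and if subjects complete greater than 70% of daily TTNS use in the 4-week period". It names no analysis set or denominator, and no analysis population is defined elsewhere in the text supplied.

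Three other sections bear on who is left to be counted:

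- Section 3.5, under the lead-in "Possible reasons for discontinuation of study intervention", has three entries, one of which is "Non-compliance". It gives no threshold or definition.
- Section 3.6: "Subjects who drop out will be replaced by recruitment from the SCI clinic". It sets no limit and does not say how a replaced subject is analysed.
- Section 11.1: "we believe 14 is sufficient and we will enrol 20 patients to account for non-compliance in the outpatient setting".

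Section 6.4 requires no final evaluation of a subject who withdraws, whatever the reason. Use of TTNS is, however, logged in the bladder diary (section 5) and collected by weekly telephone call (sections 6 and 6.4).

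**The concern.** A subject who uses the device little has a poor value on a primary outcome. Sections 3.5, 3.6 and 11.1 together allow that subject to be discontinued for it, replaced, and treated as a loss covered by over-enrolment. Discontinuation can thus depend on the outcome being measured, and section 11.2 does not require the subject who left to stay in the adherence figure.

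At stake is the feasibility/adherence verdict. The pilot is meant to inform a larger randomized trial (section 11.2). If adherence is read on those still in the study, the planners of that trial could be told that adherence was high when use across everyone who took the device home was below the protocol's own 70% mark.

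**Working it through.** **Inputs from the plan.** 20 enrolled, 14 considered sufficient (section 11.1). 4 expected to drop out or be lost (section 5). Daily use for 4 weeks, so 28 planned sessions (section 6.4). Pass marks: dropout <25% and use >70% (section 11.2).

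**Assumptions.** The 70% bar is a mean across subjects. Those removed completed on average 0% to 50% of their 28 sessions; 0% is the limiting end, since a starter has done at least one session.

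**1. The plan's own allowance.** Going from 20 to 14 is a loss of 1 − 14/20 = 30%, and 14/(1 − 0.30) = 20. The 4 expected losses in section 5 are 4/20 = 20%, which would need only 14/(1 − 0.20) = 17.5, or 18 subjects. The 30% allowance would itself fail the <25% limb if all those losses counted as dropouts. The plan does not say whether they do.

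**2. What each limb allows.** 4/20 = 20% passes the dropout limb and 5/20 = 25% fails, so at most 4 of 20 can leave. For use, 0.70 × 28 = 19.6, so 20 sessions (20/28 = 71.4%) is the smallest whole number above the bar.

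**3. Retained subjects against all starters.** With 16 retained at a mean of 20/28 and 4 removed at mean adherence *a*:

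all-starter adherence = (16 × 20/28 + 4 × *a*) / 20

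| Mean adherence of the 4 removed | All-starter adherence | Retained mean that all-starter adherence >70% would require: above (0.70 × 20 − 4*a*)/16 |
|---|---|---|
| 0% | 57.1% | 87.5% |
| 10% | 59.1% | 85.0% |
| 25% | 62.1% | 81.3% |
| 50% | 67.1% | 75.0% |

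On retained subjects both limbs pass (71.4% and 20%). Over all starters, every value in the range is below 70%.

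**4. An intermediate example (assumed sessions).** If 16 subjects complete 21 sessions and 4 stop after 6, retained adherence is 21/28 = 75%. Over all starters it is (16 × 21 + 4 × 6)/(20 × 28) = 360/560 = 64.3%.

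**5. If replacements enter the dropout denominator.** With completers at 20/28 and those removed at 0%:

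- 14 completers, 4 removed: dropout 4/18 = 22.2%; all-starter adherence (14 × 20/28)/18 = 55.6%.
- 16 completers, 5 removed: dropout 5/21 = 23.8%; adherence (16 × 20/28)/21 = 54.4%.
- 20 completers, 6 removed: dropout 6/26 = 23.1%; adherence (20 × 20/28)/26 = 54.9%.

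All three pass the dropout limb.

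**6. If withdrawals for non-compliance are not dropouts.** The dropout limb then does not restrain them. With the 6 losses that section 11.1 allows for, 14 retained at 20/28 and 6 removed at 0% give (14 × 20/28)/20 = 50%.

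**The case against.** The strongest reply is that the criterion is joint. Retention and use are separate limbs, and reporting them separately is a coherent definition of feasibility. If a withdrawal for non-compliance is a dropout, it counts against the <25% limb, and a fifth such loss among 20 fails the study. If it is not a dropout, section 3.6 does not replace that subject. Replacement and unlimited removal therefore cannot be argued together. This stands: cases 5 and 6 of the working belong to different readings. It does not close the gap, because four removals pass the dropout limb and still allow the result in step 3.

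A reader might infer that the plan reads adherence only on those who remain, so that the verdict is certainly biased upward. The documents do not say that. Section 11.2 leaves the denominator open, and sessions up to withdrawal could be counted from the diary and weekly calls.

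A reader might also infer that section 3.5 obliges the investigator to remove poor adherers. It lists possible reasons for stopping the intervention. It does not make withdrawal mandatory, say who initiates it, or remove anyone from analysis.

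It is also fair that the sessions used above are assumed, and that the 57% end is extreme: all four leavers are non-compliers with almost no use, and the rest sit near the bar. Section 3.5 has two other reasons for stopping, and the 4 losses in section 5 cover every cause. Section 11.2 may also intend a per-subject threshold. In that case no required proportion of subjects is given, and the percentages above do not apply, but the denominator is still missing.

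Finally, this is a descriptive pilot with a convenience sample, and adherence stands beside safety and satisfaction. That limits the weight of the point. The pass marks are nevertheless pre-set and attached to a primary objective.

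**Conclusion.** The point holds as a possibility that the plan leaves open, not as a demonstrated bias. As written, the >70% bar may be met after poor adherers have left and been replaced, and nothing elsewhere in the plan prevents it. With 4 of 20 removed and 16 retained averaging 20/28, the plan's limbs pass on retained subjects while all-starter adherence is 57% to 67%. This rests on the mean reading of the bar and the assumed 0% to 50% adherence of those removed. The discrepancy disappears if retained subjects use the device enough: above 87.5% on average, all-starter adherence exceeds 70% even if the four removed did almost nothing. The dropout limb is a partial safeguard, and only if withdrawals for non-compliance count as dropouts. The choice of denominator can change the feasibility verdict, so it should be fixed before data are seen.

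**What to change.** In section 11.2:

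- Compute adherence for every subject who starts home TTNS as sessions done/28, with sessions after stopping counted as not done, and apply the >70% bar to the mean over all starters. This also settles whether the bar is a mean or a per-subject threshold.
- Count withdrawals for non-compliance as dropouts.
- Keep replaced subjects in both the dropout and the adherence figures, so that replacements do not offset leavers.

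Sections 3.5, 3.6 and 11.1 must be reconciled with the compliance objective in section 2.2. A reader might conclude that non-compliance should simply be struck from section 3.5. That would change a rule for stopping the intervention, and the analysis can be repaired without it, so no particular stopping rule is proposed here.

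The cost is a few sentences. The diary and weekly calls already collect the sessions, so no extra patients or procedures are needed. The downside is that the reported adherence may be somewhat less favourable.
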